**SCHEMA**

Men ages 55 with no prior history of prostate cancer  
with normal Digital Rectal Examination (DRE)  
PSA to be performed at a Central Laboratory Facility (CLF)

Follow-up q 3 months by telephone contact and/or  
clinic visit as noted on the Study Calendar

Annual DRE and PSA  
(Prostate biopsy if abnormal DRE or elevated PSA)

For each participant, prostate biopsy at seven year anniversary following Final Enrollment.

Follow-up off-treatment as required per Appendix Section 19.10

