Participants with an elevated PSA who have benign tissue upon pathologic examination by the Pathology Core Laboratory are recommended to have a TRUS and biopsy at subsequent years if one or both of two conditions are met: (1) PSA increase of 50% or more above the PSA value that prompted the recommendation of the original biopsy or (2) adjusted PSA greater than 10 ng/ml.

PSA values will be provided for participants who are off treatment. These values will not be indexed (adjusted).

- c. All participants will be evaluated according to the AUA Symptom Scale annually.
- d. All participants will complete a diet questionnaire and have physical measurements performed at the First Annual Visit only.
- e. Participants who are removed from treatment for any reason other than development of prostate cancer will be followed twice annually for the remainder of the seven years. One contact will be by phone for a general health status update, and the other contact will be a Study Site visit for annual DRE and PSA. The requirements for endpoint reporting, management of abnormal DRE and/or "ELEVATED" PSA as well as pathology submission will be the same as for participants who remain on treatment.

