  - e. Participants found to have high grade (Grade 2 - 3) Prostatic Intraepithelial Neoplasia (PIN) at the time of biopsy should undergo an immediate rebiopsy. The rebiopsy (using the sextant biopsy technique described in Section 7.7c) must be performed within two months of the prior biopsy. If the repeat biopsy is benign or reveals PIN, the patient will continue on protocol. If this biopsy reveals prostate cancer, however, the patient is removed from protocol treatment per Section 7.14.
- 7.8 After seven years on study, all participants still receiving protocol treatment will undergo transrectal ultrasound and prostate biopsy in accordance with Sections 7.7b, 7.7c and 7.7d.
- 7.9 Development of symptoms of benign prostatic hyperplasia.

During participant on study follow-up, should obstructive symptoms develop to such an extent that the participant requests therapy, the participant should be offered therapy in accordance with standard medical or surgical practice. At the time of such therapy (including medical or surgical therapy), the manner of treatment will be recorded on study forms. One of the options for medical therapy may be finasteride. If finasteride is chosen for therapy, the participant must be evaluated and removed from protocol treatment. For this reason, other forms of medical therapy such as alpha blockade should be encouraged.

- 7.10 Upon the diagnosis of prostate cancer, staging will be accomplished in accordance with standard clinical practice (see Section 19.2). PSA values for these participants who were biopsied because of an abnormal DRE and whose biopsy is positive for prostate cancer will be provided by the Statistical Center when requested by PCPT staff. The reported PSA value for participants receiving placebo will be the measured value. The reported PSA value for participants receiving finasteride will be adjusted by a factor calculated by the Statistical Center (with monitoring by the Data and Safety Monitoring Committee).

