- 7.11 In all participants who undergo a surgical procedure in which prostate tissue is removed (e.g., prostate biopsy, TURP, radical prostatectomy), specimens will be submitted to the Pathology Core Laboratory for centralized pathology review in accordance with Section 12.0 and Appendix 19.4. The Pathology Core Laboratory will also serve as the Prostate Tissue Repository for these specimens. Sera for annual PSA determinations will be submitted to the Central Laboratory Facility; residual sera will be banked for future study in a serum bank to be maintained by the Central Laboratory Facility.
- 7.12 The Data and Safety Monitoring Committee will be charged with monitoring and evaluating potential detection bias during the study's progress. This committee may require interim DHT determinations and/or prostate biopsy (in accordance with Section 7.7) in a sample of participants to determine if such bias is operational.
- 7.13 Adherence.

Participant adherence with the medication regimen as well as the follow-up schedule is critical for proper study completion. Data Managers will contact participants every three months for the study's duration to assure medication adherence as well as to reinforce follow-up visit schedules.

Following randomization, tablet counts will occur every six months, i.e., each time the participant requires a new supply of Study Drug. All adherence information will be recorded on study forms. Details of, and procedures for, the assessments are found in the Study Manual.

7.14 Study Blinding Information and Criteria for Removal from Protocol Treatment:

- a. All participants, Study Centers, pathology and laboratory personnel will be blinded to study treatment.
- b. Laboratory and pathology specimens will be labeled by participant identification number and initials only.
- c. Participants treatment will be unblinded only if the treating physician demonstrates a compelling medical need for this information. The study drug may be discontinued without unblinding the participant.
- d. As study arms will be analyzed using an intent to treat method, participants are never "dropped" from the study.
- e. Participants will be removed from protocol treatment under the following circumstances:
  1. diagnosis of prostate cancer.
  2. initiation of treatment for benign prostatic hyperplasia (BPH) with finasteride or other 5-alpha reductase inhibitor.
  3. seven years following randomization (termination of the study).

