possible in the finasteride arm. Therefore the degree of medication adherence and contamination must be known when performing PSA assessments. The plan is to assess adherence/contamination prior to obtaining PSA specimens and to defer taking a PSA specimen in cases where there is evidence of nonadherence or contamination until there is sufficient adherence and lack of contamination. Thus, the participant is motivated to become adherent and not take open label finasteride. Also, meaningless PSA results are avoided. This strategy requires the following assumption, however:

**CRITICAL ASSUMPTION:** The procedures used to assess adherence in the individual participant at each visit where a PSA specimen is to be obtained are sufficiently sensitive and reliable to detect degrees of nonadherence affecting PSA level interpretation.

- 11.4 **SEVEN YEAR BIOPSY:** It is assumed that approximately 40% of the randomized participants will not have a prostate biopsy following seven years of study treatment and have not had a positive biopsy prior to seven years of treatment. Specifically, it is assumed there will be a 40% loss to biopsy based on the sum of 20% mortality, 15% lost to follow-up, and 5% biopsy refusals. The 20% mortality is based on an assumption that the median age at study entry will be 63 years, with the seven year U.S. (white) all-causes mortality for men that age assumed to be approximately 20%. The 15% lost to follow-up is based on experience with other prevention trials. The 5% biopsy refusal rate is based on the belief that participants who stay on the study drug for seven years will be motivated to find out whether or not they have prostate cancer.

**CRITICAL ASSUMPTION:** It is assumed that the factors affecting loss to biopsy will operate the same in both arms of the study so that the groups of participants who do not have biopsies (deaths, lost, refusal) will be comparable between the arms.

Conformity to the above assumption can be monitored by comparing between the arms the characteristics of the participants who do not have the seven year biopsy and the reason for not having the biopsy.

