#### 2.0 BACKGROUND

The Prostate Cancer Prevention Trial (PCPT) is a randomized double blind chemoprevention trial designed to test the difference in the histologically-proven prostate cancer prevalence between a group of participants taking finasteride and another taking placebo for seven years. At randomization, participants were age 55 or older with a normal DRE, no severe prostatism, a PSA  $\leq 3$  ng/ml and no prostate cancer or PIN. Participants are treated for a total of seven years with either finasteride or placebo and followed annually with a DRE and PSA. At the end of seven years, each living participant not previously diagnosed with prostate cancer will have a prostate biopsy to assess the presence or absence of prostate cancer.

Initial blood collection was specifically for the analysis of PSA and storage of serum. However, the size of this cohort provides an ideal opportunity to carry out additional research into the environmental and genetic factors which influence risk for development of prostate cancer. Some of these studies could make use of plasma and white blood cells which are not currently available from study participants. Thus, an additional blood collection will be carried out using anticoagulant so that plasma and white blood cells can be isolated. Plasma will allow the analysis of additional biomarkers such as albumin adducts, while white blood cells will provide a source of DNA. This DNA will be used (among other possible uses) for studies to investigate polymorphisms in genes which may influence prostate cancer risk. For example, interindividual differences in carcinogen or hormone metabolism, related to polymorphisms in specific genes, can be determined by polymerase chain reaction-restriction fragment length polymorphism analysis of DNA. Similarly, polymorphisms in genes responsible for detoxification of carcinogens or DNA repair can also be analyzed.

This appendix is intended to provide the rationale and procedures for the additional voluntary submission of white blood cells for future analyses. These samples, as well as the serums for annual PSA analysis and banking and tissue from all prostate procedures, are an invaluable resource for investigations into cancer etiology and prevention.

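### The protocol contradicts itself on whether men who have stopped study drug get the seven-year endpoint biopsy, and under the narrower rule they would enter the primary analysis essentially only as cancer cases

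*Supplement*

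**What the plan says.** Two sets of current passages disagree.

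**Narrow rule.** Section 7.8: "After seven years on study, all participants still receiving protocol treatment will undergo transrectal ultrasound and prostate biopsy". Section 7.6e covers men who have stopped drug: "Participants who are removed from treatment for any reason other than development of prostate cancer will be followed twice annually" until year seven. One yearly contact is by telephone and "the other contact will be a Study Site visit for annual DRE and PSA". Abnormal results are managed, and endpoints reported, as for men on drug. No seven-year biopsy is listed.

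**Broad rule.** The Schema: "For each participant, prostate biopsy at seven year anniversary following Final Enrollment". The Background account of the final design relies on a final biopsy of all men to limit detection bias. Section 11.1 schedules the biopsy for the men randomised. Appendix 19.9: "each living participant not previously diagnosed with prostate cancer will have a prostate biopsy". Appendix 19.10 schedules it for all men not already diagnosed. The Study Calendar marks it at the seven-year visit with no on-drug condition.

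**Analysis.** Section 11.9 includes everyone with a seven-year biopsy plus men with histologically proven cancer before then. Section 7.14d: "As study arms will be analyzed using an intent to treat method", adding that nobody is dropped. Section 11.4 budgets for "a 40% loss to biopsy based on the sum of 20% mortality, 15% lost to follow-up, and 5% biopsy refusals" and makes it a critical assumption that these losses act alike in both arms.

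**The concern.** The final biopsy is the design's main protection against unequal detection. Under 7.8 it would be withheld from a group defined by what happened after randomisation. Combined with 11.9, an off-treatment man whose cancer is found by PSA, DRE or TURP counts as a case. An off-treatment man without a diagnosis ordinarily has no endpoint and drops out of the denominator.

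The documents give reasons why stopping could differ by arm. Unacceptable side effects are grounds for removal (7.14e.5), and Figure 1 shows more decreased libido (4.7% vs 1.3%) and ejaculatory disorder (4.4% vs 1.7%) on finasteride 5 mg. Starting a 5-alpha reductase inhibitor for BPH is also grounds for removal (7.14e.2), and Section 11.6 considers that BPH may be commoner on placebo. Early detection among stoppers could differ too, because 7.6b reports off-treatment PSA without the index adjustment, including for men who have moved to open-label finasteride.

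At stake are the comparability assumption of 11.4, the intent-to-treat statement of 7.14d, and the number of evaluable men.

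**Working it through.** **1. Reproduce the plan's power (Sections 11.7 and 11.10).** Inputs: 9,000 per arm, 60% evaluable (5,400), placebo rate 6%, unadjusted reduction 30% (so 4.2% on finasteride), contamination 5%, nonadherence 14%, two-sided 5%.

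- p0r = 0.95 × 0.06 + 0.05 × 0.042 = 0.0591
- p1r = 0.14 × 0.06 + 0.86 × 0.042 = 0.04452
- Adjusted reduction = (0.0591 − 0.04452)/0.0591 = 24.7%
- Power: 92.8% by the usual two-proportion formula, 92.2% with continuity correction. The plan states 92.1%, so it is reproduced.

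**2. Model of the literal 7.8 rule.** Let q be the off-treatment share of otherwise evaluable men, and f the share of their cancers found by year seven without the final biopsy. The documents give neither. I assume q of 10-30% and f of 20-50%. For a true rate p, per arm:

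- cases = 5,400 × [(1 − q)p + q f p]
- analysed = 5,400 × [(1 − q) + q f p]

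**3. No true effect (6% in both arms).** Worked example with f = 0.5:

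- q = 10%: 307.8/4,876.2 = 6.31%
- q = 20%: 291.6/4,352.4 = 6.70%
- ratio = 1.061

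| Off drug, placebo vs finasteride | Ratio, f = 20% to 50% | Two-sided rejection |
|---|---|---|
| 10% vs 10% | 1.000 | 5.0% |
| 20% vs 20% | 1.000 | 5.0% |
| 10% vs 15% | 1.012-1.029 | 5.3-6.5% |
| 10% vs 20% | 1.025-1.061 | 6.1-11.7% |
| 20% vs 30% | 1.032-1.074 | 6.6-14.2% |

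More stopping on finasteride biases against finasteride. More stopping on placebo does the reverse.

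**4. Equal stopping, planned effect (5.91% vs 4.452%).** Power starts at 92.8%.

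| Off drug, both arms | Power, f = 20% to 50% |
|---|---|
| 10% | 90.6-91.4% |
| 20% | 87.9-89.9% |
| 30% | 84.5-88.0% |

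The relative reduction barely moves (24.7% to 24.4-24.6%).

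**5. Which rule does the planning text assume?** The loss budget is 20% + 15% + 5% = 40%. It leaves no share for men who are alive and followed but off drug, which fits the broad rule. The 5% refusal rate, however, is argued from men who remain on drug for seven years, which fits 7.8. The planning text does not settle the question.

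**The case against.** The strongest reply is that 7.8 is the outlier. The Schema, Background, Section 11.1, the Study Calendar and Appendices 19.9 and 19.10 put no on-drug condition on the biopsy, and Appendix 19.10 came in with the last numbered amendment. Section 7.6e equates endpoint reporting for men on and off drug, and further off-treatment instructions sit in a Study Manual that is not available here. Section 11.9 has no on-drug condition either, so a stopper biopsied under the Schema with a negative result is a valid non-case. Even under 7.8, a negative for-cause biopsy at the seventh annual visit might qualify. All of this stands. It is why the finding is a contradiction, and why the wording is essentially only as cases.

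Four stronger readings are tempting and not supported:

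- **The design restricts the endpoint biopsy to men on drug.** Only 7.8 says so.
- **The comparison becomes as-treated.** Men stay in their randomised arm. This is selection into the analysed set, and 11.9 already leaves out a planned 40% under a declared assumption.
- **The result is biased.** Bias needs unequal stopping or unequal off-treatment detection. The two mechanisms above push in opposite directions, and no document figure supports a 10-point gap. The discontinuation figures given are small (1.6% stopping finasteride for adverse experience over a median of 322 days), though far shorter than seven years. The run-in also screens out poor adherers.
- **The 5,400 per arm cannot be reached.** That follows only if 7.8 is applied literally.

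A cruder model might also be tried: 3% diagnosed early, 3% positive at year seven, and 60% applied only to undiagnosed men. It gives a ratio of 1.074 for 10% vs 20% off drug. But with nobody off drug it already yields (270 + 162)/(270 + 5,238) = 7.84% instead of 6%, so it mixes the 40% loss with the effect of 7.8.

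Finally, 11.4 provides for comparing unbiopsied men and their reasons by arm, and the monitoring committee reviews the critical assumptions. That would help detect a problem. It does not tell sites which rule to follow.

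**Conclusion.** The contradiction is in the text and concerns who receives the primary-endpoint assessment. It needs resolving. Its consequences are conditional on sites applying 7.8 literally.

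In that case 7.8 adds treatment-dependent selection to the planned 40% loss, conflicts with 7.14d and threatens the 11.4 assumption. At an assumed 10% vs 20% off drug, the spurious excess is roughly 3-6% with type I error of about 6-12%, against a planned adjusted reduction of 24.7%. At equal shares there is no bias under the null in this model. Power stays above the 90% target at 10% off drug and falls just below it at 20%. If every undiagnosed man is biopsied, as most passages say, the stated 92.1% is unaffected.

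The off-treatment shares and early-detection fractions are assumptions. The model also gives off-treatment men the same underlying cancer risk, and the null calculations use the same early detection in both arms.

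**What to change.** Reconcile 7.8 and 7.6e with the Schema, Section 11.1 and Appendices 19.9 and 19.10, so that one rule defines who is scheduled for the endpoint biopsy. That rule should be consistent with the intent-to-treat statement in 7.14d and the loss budget in 11.4. Record on- or off-treatment status at year seven, and report biopsy uptake by arm and by that status alongside the comparison already foreseen in 11.4.

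The cost is amendment wording, one recorded item and one table. Reconciling to the Schema and the 60% planning figure adds no biopsies beyond those they already count.

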**Committee will monitor relative rate of these events for trends.**

- 5. unacceptable side effects. The reason(s) must be documented on the study forms.
  - 6. missed contacts. The participant missed receiving more than two consecutive bottles of study drug or missed more than four consecutive Study Site Visits.
  - f. Participants may be returned to protocol treatment (i.e., reactivated) if they meet the criteria for reactivation defined in Section 4.0 of the Study Manual.
- 7.15 The participant may withdraw from the study at any time for any reason. The reason must be documented in the study forms.
- 7.16 All participants will be followed off-treatment as required per Appendix Section 19.10.

**8.0 TOXICITIES TO BE MONITORED AND DOSAGE MODIFICATIONS**

- 8.1 There will be no modifications to the study drug dose.
- 8.2 For decreased libido, impotence and decreased volume of ejaculate or any clinically acceptable symptoms potentially due to the study drug, participants should be requested to remain on study drug. If they refuse, they may be allowed to discontinue the drug. They should then be reassessed in three months. If the side effect has not resolved, the participants can restart the drug. If the side-effects improve, the participants should be re-challenged with the drug and if the side effect recurs, the drug should be discontinued permanently.

The PCPT will not use the new NCI Common Toxicity Criteria for the reporting of Adverse Drug Reactions/Adverse Events and routine follow-up. Please use the Southwest Oncology Group Toxicity Criteria in Appendix 19.1 for: 1) assessment of all symptoms (including those related to sexual function) for the purpose of reporting Adverse Drug Reactions/Adverse Event and for 2) assessment of symptoms not related to sexual function for routine toxicity reporting. For assessment of symptoms of sexual function for eligibility purposes and routine toxicity reporting, use the following criteria in lieu of those in Appendix 19.1.

Impotence:

- Grade 1 decrease in normal function, able with difficulty to achieve vaginal penetration.
- Grade 3 absence of function, no erections

Loss of Libido:

- Grade 1 minimal decrease in desire for sexual activity, no impact on frequency of intercourse
- Grade 2 moderate decrease in desire for sexual activity, minimal impact on frequency of intercourse
- Grade 3 moderate to severe decrease in desire for sexual activity, moderate impact on frequency of intercourse
- Grade 4 no desire for sexual activity, no intercourse

Ejaculate Volume:

- Grade 1 less than 1/3 reduction in ejaculate volume (as perceived by the participant)
- Grade 2 1/3 to 2/3 reduction in ejaculate volume
- Grade 3 greater than 2/3 reduction in ejaculate volume
- Grade 4 no ejaculate

- 8.3 Unexpected or fatal toxicities (including suspected reactions) must be reported to the Southwest Oncology Group Operations Office, and to the IRB. The procedure for reporting adverse reactions is outlined in Section 16.0.

## 9.0 STUDY CALENDAR

REQUIRED STUDIES	Enrollment	Randomization	Post-Randomization Follow-Up				
	1st visit	2nd visit	3 and 9 month phone calls	6 month visits	Annual visits	Seven yr visit	Extended Follow-Up†
Participant Demographics	X						
Contact Information	X	X	X	X	X	X	X
MEDICAL HISTORY							
Cancer	X						
Prior therapy	X						
Family history prostate cancer	X						
CHD risk factors f	X						
Participant Lifestyles							
Smoking	X						
Alcohol Use	X						
Eating	X						
Exercise	X						
QOL - Health Survey SF-36	X			X*	X	X	
Food Frequency Questionnaire					X		
Participant Report							
Urinary symptoms	X	X		X*	X	X	X
Sexual functioning	X	X		X*	X	X	X
Staff Report							
Adherence assessment		X		X	X	X	
Symptom/side effects assess.		X		X	X	X	
CLINICAL							
Performance Status	X						
Current medications	X	X	X	X	X	X	
DRE	X				X	X	X†
Physical Examination	X				X	X	X†
Anthropometric measurements					X		
Prostate biopsy/TRUS					X#	X	
LABORATORY							
Serum for PSA/cholesterol/ and serum bank storage	X£				X£	X£	X†
WBC Blood draw							
Outcome Assessment							
Prostate Cancer		X		X	X	X	X
BPH		X		X	X	X	X
Other Cancer		X		X	X	X	X
Cardiovascular event		X		X	X	X	X
Death		X		X	X	X	X
TREATMENT							
Finasteride or matched Placebo		X	X	X	X		
Enrollment drug	X						

NOTE: All forms to be utilized for this study and forms submission guidelines are found in the Study Manual.

*f* See Section 19.3 for CHD risk factors.

\* Collected at first six month visit and then annually.

Collected only at first Annual Visit.

With measurement of prostate size.

# Performed only on participants whose PSA or DRE indicate; pathology submission is required.

£ Specimen mailed to and tests performed in Central Laboratory Facility (CLF).

Non-fasting total cholesterol performed on serum drawn at the first visit only. If total cholesterol exceeds 200 mg/dl, patient referral for evaluation is required (see Study Manual).

As outlined in Section 19.9.

† See Section 19.10 for the procedures related to Extended Follow-Up.

